6.2.2. Laboratory Safety Tests

Safety laboratory tests will be performed as described in the protocol.

To determine if there are any clinically significant laboratory abnormalities, the haematological, clinical chemistry (serum) and urinalysis safety tests will be assessed against the criteria specified in the sponsor reporting standards. The assessment will take into account whether each subject's baseline test result is within or outside the laboratory reference range for the particular laboratory parameter.

Baseline is defined as the last predose measurement taken in each study period.

6.2.3. Vital Signs Data

Supine measurements will be taken at times detailed in the Schedule of Activities given in the protocol.

Baseline is the last predose recording in each study period.

6.2.4. ECG Results

QT interval, QTc, PR, RR, QRS and heart rate will be recorded at each assessment time indicated in the Schedule of Activities given in the protocol.

If not supplied, QTcF will be derived using Fridericia's heart rate correction formula:

$$\text{QTcF} = \text{QT} / (\text{RR})^{1/3} \quad \text{where RR} = 60/\text{HR} \text{ (if not provided)}$$

Baseline is the last predose recording in each study period.

The average of the triplicate measurements will be calculated prior to analyzing the data. Baseline will be defined as the average of the triplicate predose recordings in each study period.

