1.3. Schedule of Activities (SoA)

The SoA table provides an overview of the protocol visits and procedures. Refer to the STUDY ASSESSMENTS AND PROCEDURES section (Section 8) of the protocol for detailed information on each procedure and assessment required for compliance with the protocol.

The investigator may schedule visits (unplanned visits) in addition to those listed in the SoA table, in order to conduct evaluations or assessments required to protect the well-being of the participant.

Table 1.Schedule of Activities

Visit Identifier	Screening			Period 1			Period 2 ^a			ЕТ	Phone call
Days Relative to Day 1	-28 to -2	-1	1	2	3	4	1	2	3		28-35 days after last dose of metformin ^b
Informed Consent	Х										
Inclusion/Exclusion Criteria	Х	Х									
Medical, Drug, Tobacco and Alcohol History	Х										
Complete Physical Examination ^c		Х									
Demography, Height and Weigh	Х										
Serum FSH (Postmenopausal Females Only)	Х										
Serum Pregnancy Test (HCG) for WOCBP only	Х	Х							Х	Х	
Blood sampling for Pfizer Prep D1 banked sample(s) ^d			Х								
Urine Drug Screen	Х	Х									
Single 12-Lead ECG	Х		X ^e				X ^e		Х	Х	
Clinical Safety Labs (Blood and Urine)	Х	Х				Xf			Х	Х	
Contraception check	Х	Х							Х	Х	Х
Serology: HIV, HepBsAg, HepBcAb, HepBsAb, HCVAb testing	Х										
QuantiFERON [®] - TB Gold Test	Х										
Vital Signs and Oral Temperature	Х		X ^g				X ^g		Х	Х	
Moderate Fat Meal consumed prior to dosing			Х				Х				
Metformin Dosing ^h			Х				Х				
PF-04965842 Dosing (Sequence 1)							Х	Х			
PF-04965842 Dosing (Sequence 2)			Х	Х							
Metformin PK Blood Sampling			X ⁱ	\rightarrow	X ⁱ		X ⁱ	\rightarrow	X ⁱ		
Metformin PK Urine Sampling			X ⁱ	\rightarrow	X ⁱ		X ⁱ	\rightarrow	X ⁱ		
NMN PK Blood Sampling			X ⁱ	X ⁱ			X ⁱ	X ⁱ			

Table 1.Schedule of Activities

Visit Identifier	Screening	Period 1		Period 2 ^a			ET	Phone call			
Days Relative to Day 1	-28 to -2	-1	1	2	3	4	1	2	3		28-35 days after last dose of metformin ^b
NMN PK Urine Sampling			X ⁱ	X ⁱ			X ⁱ	X ⁱ			
CRU Confinement		Х	\rightarrow	\rightarrow	\rightarrow	\rightarrow	\rightarrow	\rightarrow	Х		
Serious and non-serious Adverse Event Monitoring	Х	\rightarrow	\rightarrow	\rightarrow	\rightarrow	\rightarrow	\rightarrow	\rightarrow	\rightarrow	\rightarrow	Х
Prior/Concomitant Treatment Assessment	Х	\rightarrow	\rightarrow	\rightarrow	\rightarrow	\rightarrow	\rightarrow	\rightarrow	\rightarrow	\rightarrow	Х

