Abbreviations: \rightarrow = ongoing/continuous event; CRU = clinical research unit; ECG = electrocardiogram; ET = early termination; FSH = follicle-stimulating hormone; HepBcAb = hepatitis B core antibody; HepBsAb = hepatitis B surface antibody; HepBsAg = hepatitis B surface antigen; HCVAb = hepatitis C antibody; HCG = Human Chorionic Gonadotropin; HIV = human immunodeficiency virus; hr = hour; NMN = N¹-methylnicotinamide; PK = pharmacokinetic; TB = tuberculosis; WOCBP = women of childbearing potential.

a. Day 1 of Period 2 will be at least 4 days after Day 1 of Period 1.

b. Phone contact to capture any potential AEs and concomitant treatment(s) and to confirm appropriate contraception usage.

c. After the complete physical examination on Day -1, further examinations will be performed at the discretion of the investigator.

d. If not collected on the designated collection day, collect at the next available time point when biospecimens are being collected in conjunction with a participant visit.

e. Perform single 12 lead ECG at pre-dose (before meal) and 2 hours post-dose.

f. Clinical safety labs will be collected before Period 2 Day 1.

g. Supine blood pressure, pulse rate and oral temperature pre dose and 2 hr post dose.

h. Participants will be dosed with metformin following a moderate-fat breakfast at approximately 08:00 AM (±2 hrs). On the day of co administration of metformin and PF-04965842, metformin will be administered with PF-04965842 concomitantly in no specific order, over no more than 5 minutes apart.

i. See pharmacokinetic sampling schema. (Table 2).

Table 2. Pharmacokinetic Sampling Schema

	Periods 1 and 2											
Visit Identifier	Day 1							Da	Day 2			
Hours After Dose on Day 1	0 ^a	0.5	1	2	4	6	8	12	16	24	36	48
Blood samples for												
PK blood sampling for metformin	X ^a	Х	Х	Х	Х	Х	Х	Х	Х	Х	Х	Х
PK blood sampling for NMN	X ^a	Х	Х	Х	Х	Х	Х	Х	Х	Х		
Urine samples for												
Predose PK spot urine blank	X ^a											
Start/Stop PK Urine collection for metformin concentrations ^{b,c}	Х←							\rightarrow X \leftarrow		→Х←	$\rightarrow X \leftarrow$	→Х
Start/Stop PK Urine collection for NMN ^{b,d}	Х←							→Х←		→Х		

Abbreviations: NMN = N1-methylnicotinamide; PK = pharmacokinetic.

a. Predose (metformin administration) sample collection.

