If a participant meets **any** of these criteria, the BP should be repeated 2 more times and the average of the 3 BP values should be used to determine the participant's eligibility.

- 11. Screening supine 12-lead ECG demonstrating:
 - QTcF >450 msec OR
 - QRS interval >120 msec.
- 12. If QTcF exceeds 450 msec, or QRS exceeds 120 msec, the ECG should be repeated 2 more times and the average of the 3 QTcF or QRS values should be used to determine the participant's eligibility. Computer-interpreted ECGs should be overread by a physician experienced in reading ECGs before excluding participants.
- 13. Participants with ANY of the following abnormalities in clinical laboratory tests at screening, as assessed by the study-specific laboratory and confirmed by a single repeat test, if deemed necessary:
 - Aspartate aminotransferase (AST)/serum glutamic oxaloacetic transaminase (SGOT) or alanine aminotransferase (ALT)/serum glutamic pyruvic transaminase (SGPT) level ≥1.5 × upper limit of normal (ULN).
 - Total bilirubin level >1.0 × ULN; participants with a history of Gilbert's syndrome may have direct bilirubin measured and would be eligible for this study provided the direct bilirubin level is $\leq 1.0 \times$ ULN.
 - Prothrombin Time (PT)/International Normalized Ratio (INR) or partial thromboplastin time (PTT)/activated partial thromboplastin time (aPTT) >1.0 × ULN.
 - Estimated creatinine clearance <90 mL/min (see Appendix 2 for Cockcroft-Gault formula).

Other Exclusions:

- 14. History of regular alcohol consumption exceeding 14 drinks/week for female participants or 21 drinks/week for male participants (1 drink = 5 ounces [150 mL] of wine or 12 ounces [360 mL] of beer or 1.5 ounces [45 mL] of hard liquor) within 6 months before screening.
- 15. Known relevant history of elevated liver function tests (LFTs).
- 16. History of tuberculosis (TB) (active or latent) or inadequately treated TB infection. Positive QuantiFERON[®] TB Gold test.
- 17. Any history of chronic infections, any history of recurrent infections, any history of latent infections, or any acute infection within 2 weeks of baseline.
- 18. History of disseminated herpes zoster, or disseminated herpes simplex, or recurrent localized dermatomal herpes zoster.

- 19. History of sensitivity to heparin or heparin-induced thrombocytopenia.
- 20. Use of tobacco- or nicotine- containing products in excess of the equivalent of 5 cigarettes per day.

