8.2.3. Electrocardiograms

Single 12-Lead ECGs should be collected at times specified in the Table 1 of this protocol.

All scheduled ECGs should be performed after the participant has rested quietly for at least 10 minutes in a supine position. Supine body position with fully lowered headrest should be consistently maintained for each ECG performed. Environmental distractions in the clinic (TV, radio, conversation) and other study procedures (eg, BP measurement, PK sampling) during both the pre-ECG rest and the ECG recording period must be minimized. In particular, changes in heart rate should be avoided. Whenever the nominal time points for different procedures coincide, the ECGs should always be collected prior to any other procedures (including vital signs and blood collection). ECGs should not be collected approximately within 2 hours of a meal in order to avoid the effect of food intake on the ECG. The time of meals must be standardized (±15 minutes) between study days and study periods (see also the Section 5.3).

To ensure safety of the participants, a qualified individual at the investigator site will make comparisons to baseline measurements from the current period. Additional ECG monitoring will occur if a) a postdose corrected QT interval (QTc) interval is increased by \geq 30 msec from the baseline and is >450 msec; or b) an absolute QTc value is \geq 500 msec for any scheduled ECG. If either of these conditions occurs, then 2 additional ECGs will be collected approximately 2 to 4 minutes apart to confirm the original measurement. If the QTc values from these repeated ECGs remain above the threshold value, then a single ECG must be repeated at least hourly until QTc values from 2 successive ECGs fall below the threshold value that triggered the repeat measurement.

If a postdose QTc interval remains \geq 30 msec from the baseline and is >450 msec; or b) an absolute QTc value is \geq 500 msec for any scheduled ECG for greater than 4 hours (or sooner, at the discretion of the investigator), or QTc intervals get progressively longer, the participant should undergo continuous ECG monitoring. A cardiologist should be consulted if QTc intervals do not return to less than the criterion listed above after 8 hours of monitoring (or sooner, at the discretion of the investigator).

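### Does the triplicate-ECG wording in SAP 6.2.4 conflict with the protocol's single-ECG schedule in a way that affects the analysis?

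*SAP*

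**What the plan says.** SAP 6.2.4 takes its ECG times from the protocol: the intervals "will be recorded at each assessment time indicated in the Schedule of Activities given in the protocol". It then defines baseline: "Baseline is the last predose recording in each study period". The paragraph after that adds "The average of the triplicate measurements will be calculated prior to analyzing the data" and defines baseline again: "Baseline will be defined as the average of the triplicate predose recordings in each study period". SAP 8.3.7 uses this baseline for the change-from-baseline summaries and refers the reader back to 6.2.4. The same section tabulates maximum postdose QTc and maximum increase by category.

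The protocol schedules no triplicates. The row in Table 1 (section 1.3) is "Single 12-Lead ECG", footnote e says "Perform single 12 lead ECG at pre-dose (before meal) and 2 hours post-dose", and section 8.2.3 says "Single 12-Lead ECGs should be collected at times specified in the Table 1 of this protocol". The only average of three ECGs that the protocol defines is at screening, in exclusion criterion 12, where "the average of the 3 QTcF or QRS values should be used to determine the participant's eligibility". Section 8.2.3 also provides for unscheduled recordings: two confirmatory ECGs when a QTc threshold is met, at least hourly ECGs if the value stays above it, and discretionary repeats where lead placement is in doubt.

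**The concern.** A section with two baseline definitions is normally a defect, because an analyst could use either and obtain different changes from baseline. Here one of them also calls for data that the protocol does not collect. Read literally, the SAP describes the analysed ECG values as means of three recordings, when each scheduled value is one recording.

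There is a second strand. An original ECG plus two confirmatory ECGs makes three recordings, and the SAP does not say whether such a set is averaged, reduced to its highest or last value, or only listed. If the averaging sentence were applied to it, a participant could move between cells of the QTc category table. At stake would be the accuracy of the ECG safety description.

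**Working it through.** The plan states no figure that depends on this point, so there is none to reproduce. The check is a count of the recordings on which the wording could act.

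**1. Scheduled ECGs.** Inputs: 12 participants, 6 per sequence (Protocol 4.1). ECGs are taken predose and 2 h postdose on Day 1 of each period, and once on Period 2 Day 3 (Protocol Table 1, footnote e). Screening and early-termination ECGs are left out, and all 12 are assumed to complete.

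- Predose: 12 × 2 periods = 24.
- Postdose: 12 (Period 1, 2 h) + 12 (Period 2, 2 h) + 12 (Period 2 Day 3) = 36.
- Total: 24 + 36 = 60, of which 0 are triplicate.
- Postdose by treatment: A = 6 × 1 + 6 × 2 = 18; B = 6 × 1 + 6 × 2 = 18. Each sequence has its second treatment in Period 2, where there are two postdose ECGs.

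**2. Baseline under each definition.** Let x be the one predose recording in a period. The last predose recording is x. The average of what is available is x/1 = x. The difference is 0 for all 24 predose values. A strict reader would say that a triplicate average cannot be formed from one recording; then only the last-predose definition can be used, and the baseline is again x.

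**3. Postdose values.** The same argument applies: one recording per scheduled time, so the averaging sentence leaves all 36 unchanged.

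**4. Where the wording could matter.** Only repeats remain.

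- *Predose repeats.* The last-predose definition, which SAP 6.2.2 and 6.2.3 also use for laboratory tests and vital signs, gives an answer. The two ECG definitions would differ only if three predose recordings existed, for instance after a predose QTc of 500 msec or more. Exclusion criterion 11 bars a screening QTcF above 450 msec, so this should be very unusual.
- *Hourly repeats.* SAP 6.2.4 ties ECG values to the times in the Schedule of Activities. Hourly alarm ECGs are not at those times, so the natural reading keeps them out of the by-time summaries.
- *Maximum table.* A maximum postdose QTc, in ordinary usage, is the highest postdose value. The SAP does not say explicitly whether unscheduled values count.
- *Postdose confirmatory sets and lead-placement repeats at a scheduled time.* These are truly unaddressed.

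**5. How much the convention could matter in one participant.** Assumed values, for illustration only: baseline 448 msec, postdose 482 msec, repeats 446 and 444 msec. The first alarm condition in Protocol 8.2.3 is met, since 482 − 448 = 34 ≥ 30 and 482 > 450.

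| Convention | QTc (msec) | Change (msec) | Category (SAP 8.3.7) |
|---|---|---|---|
| Highest | 482 | +34 | moderate on both |
| Mean of three | (482 + 446 + 444)/3 = 457.3 | +9.3 | mild; none |
| Last | 444 | −4 | none; none |

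The convention can therefore move one participant in a descriptive table, but only after an alarm has occurred.

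**The case for a change.** The best argument for acting is that the stray sentence and the silence on repeats can combine. The averaging sentence is the only SAP text that could be read as governing a set of three recordings. Applied to a confirmatory set, it would dilute the reading that raised the alarm, as the table shows. Deciding beforehand costs a sentence or two and removes any suspicion of choosing after seeing the data. The SAP's statistical methods may also be published with the study report, where the triplicate wording would misdescribe the data.

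Part of this stands. The text is inconsistent, SAP section 1 records no amendments, so this is current wording, and postdose confirmatory sets have no written rule. The consequences are small, however. Alarms are raised at the site against the current period's baseline (Protocol 8.2.3), so SAP averaging cannot suppress one. SAP 8.3.7 has the ECG data listed as well as tabulated. SAP 4.2 states that there are no decision rules. The publication argument is weak, because the protocol is listed among the same published appendices (Protocol 10.1.5) and shows the single-ECG schedule. The documents give no rate for triggered repeats under this regimen; the QTc counts from earlier studies in Protocol 2.2.4.1 involve other doses and cannot supply one.

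**Conclusion.** No change to the plan follows. The triplicate wording is a clerical slip: it changes 0 of 60 scheduled ECG values, and an analyst with the protocol in hand will use the one predose recording as baseline. The silence on postdose repeats is missing detail of the kind that analysts fill sensibly, by keeping unscheduled recordings out of the by-time summaries and reporting the highest postdose value in the maximum table. Tidying the two sentences would be harmless, but no conclusion depends on it.

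This rests on three assumptions: that ECGs are taken as scheduled, once per time point; that repeats are few, which the documents make plausible but do not quantify; and that the ECG tables stay descriptive. Metformin renal clearance and the other pharmacokinetic comparisons are unaffected in any case.

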6.2.5. Other Safety Data

Additional safety data will be collected as described in the protocol and will be listed if collected in the sponsor's database.

6.3. Other Endpoints

6.3.1. PK Endpoints

PK analysis of metformin and NMN (N1-methylnicotinamide) will be taken according to the Schedule of Activities given in the protocol.

The following PK parameters will be calculated by treatment and by analyte (if applicable) from the concentration-time data and urine concentrations using standard noncompartmental methods:

Table 2. Noncompartmental PK Parameters

PK Parameter	Analysis Scale	Metformin	NMN (N1-methylnicotinamide)
AUC _{inf} [*]	ln	A, D	
AUC _{last}	ln	A, D	D
AUC ₂₄	ln	D	A, D
C _{max}	ln	A, D	A, D
T _{max}	R	D	D
t _{1/2} [*]	R	D	
CL/F [*]	ln	D	
V/F*	ln	D	
Ae [*]	R	D	D
Ae% [*]	R	D	
CL _r [*]	ln	A, D	A, D

Key: A=analyzed using statistical model, D=displayed with descriptive statistics, ln=natural-log transformed, R=raw (untransformed), *=if data permits

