Preclinical in vitro inhibition studies showed that the unbound maximum observed concentration $(C_{max})/50\%$ inhibitory concentration (IC50) ratio is 0.24 and 0.13 for multidrug and toxic compound extrusion transporter (MATE)1 and MATE2K, respectively, suggesting that PF-04965842 has a potential to inhibit these drug transporters in vivo as ratios exceed the in vitro regulatory threshold unbound C_{max}/IC_{50} ratio of 0.02.⁸ Therefore, a clinical interaction study with a sensitive MATE1 and MATE2K substrate is needed to assess the effect of PF-04965842 on the activity of these transporters. The primary purpose of this study is to assess the effect of PF-04965842 on the in vivo pharmacokinetics (PK) of metformin, a sensitive substrate for MATE1 and MATE2K.⁸ Metformin is also a substrate for organic cation transporter (OCT)1 and OCT2. However, PF-04965842 is not an inhibitor of OCT2 (C_{max}/IC50 ratio is >300) and despite the unbound PF-04965842 C_{max}/IC50 ratio for OCT1 being just above 0.02 (0.03), inhibition of OCT1, a hepatic uptake transporter, is not expected to increase plasma metformin exposures as OCT1 does not modulate metformin clearance as it is primarily excreted unchanged in urine. Both MATE1 and MATE2K are renal transporters that are expressed in the apical membrane of the renal proximal tubules thus play an important role in tubular secretion and reabsorption of drug molecules in the kidney. Therefore, significant MATE1/2K inhibition would primarily impact the renal clearance of substrates for these transporters with having minimal effects, if any, on plasma exposures.

 N^{1} -methylnicotinamide (NMN), a metabolite of niacin, has been reported to be an endogenous biomarker for assessing MATE/OCT2 inhibition. Renal clearance of NMN was shown to be reduced by ~70% by pyrimethamine, a potent MATE/OCT2 inhibitor.⁹ As such, NMN is being assessed in this study to further investigate the utility of this endogenous substance as a biomarker for MATE activity in comparison to metformin, the gold standard for assessing MATE activity in drug-drug interaction (DDI) studies.⁸

Objectives and Endpoints

Objectives:	Endpoints:
Primary:	Primary:
• To estimate the effect of PF-04965842 on MATE1/2K activity via the pharmacokinetic assessment of a single, oral dose of metformin in healthy participants.	Metformin CL _{r.}
Secondary:	Secondary:

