4.2. Scientific Rationale for Study Design

In preclinical in vitro inhibition studies, the potential for PF-04965842 to inhibit MATE1 and MATE2K was assessed. A steady-state total C_{max} of PF-04965842 was 3.7 μ M (1199 ng/mL) at a maximum clinical dose of 200 mg daily and unbound C_{max}/IC_{50} ratio is 0.24 and 0.13 for MATE1 and MATE2K, respectively, suggesting that PF-04965842 has a potential to inhibit these drug transporters in vivo as ratios exceed the in vitro regulatory threshold unbound C_{max}/IC_{50} ratio of 0.02.⁸

Therefore, a clinical interaction study with a sensitive MATE1 and MATE2K substrate is needed to assess the effect of PF-04965842 on the activity of these transporters. The primary purpose of this study is to assess the effect of PF-04965842 on the in vivo pharmacokinetics (PK) of metformin, a sensitive substrate for MATE1 and MATE2K.⁸ Metformin is also a substrate for organic cation transporter (OCT)1 and OCT2 however PF-04965842 is not an inhibitor of OCT2 (C_{max}/IC_{50} ratio is >300) and despite the unbound PF-04965842 C_{max}/IC_{50} ratio for OCT1 is just above 0.02 (0.03), inhibition of OCT1, a hepatic uptake transporter, is not expected to increase plasma metformin exposures as OCT1 does not modulate metformin clearance as it is primarily excreted unchanged in urine. Both MATE1 and MATE2K are renal transporters that are expressed in the apical membrane of the renal proximal tubules thus play an important role in tubular secretion and reabsorption of drug molecules in the kidney. Therefore, significant MATE1/2K inhibition would primarily impact the renal clearance of substrates for these transporters with having minimal effects, if any, on plasma exposures.

NMN, a metabolite of niacin, has been reported to be an endogenous biomarker for assessing MATE/OCT2 inhibition. Renal clearance of NMN was shown to be reduced by ~70% by pyrimethamine, a potent MATE/OCT2 inhibitor.⁹ As such, NMN is being assessed in this study to further investigate the utility of this endogenous substance as a biomarker for MATE

activity in comparison to metform in, the gold standard for assessing MATE activity in DDI studies.⁸

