9.4.4.2. Derivation of Pharmacokinetic Parameters Prior to Analysis

PK parameters for metformin and NMN will be derived from the plasma concentration-time profiles and urine concentrations as shown below in Table 6.

Parameter	Definition	Method of Determination	Analyte
AUC ₂₄	Area under the plasma concentration-time profile from time zero to 24 hours	Linear/Log trapezoidal method.	N
AUC _{last}	Area under the plasma concentration-time profile from time zero to the time of the last quantifiable concentration (C_{last})	Linear/Log trapezoidal method.	N, M
AUC _{inf} ^a	Area under the plasma concentration-time profile from time zero extrapolated to infinity	$AUC_{last} + (C_{last}*/k_{el}),$ where $C_{last}*$ is the predicted plasma concentration at the last quantifiable time point estimated from the log-linear regression analysis.	Μ
C _{max} T _{max}	Maximum plasma concentration Time for C_{max}	Observed directly from data. Observed directly from data as time of first occurrence.	N, M N, M
$\mathbf{t}_{1_2}^{'}$	Terminal elimination half-life	$Log_e(2)/k_{el}$, where k_{el} is the terminal phase rate constant calculated by a linear regression of the log-linear concentration-time curve. Only those data points judged to describe the terminal log-linear decline will be used in the regression.	Μ
CL/F	Apparent clearance for extravascular dosing	Dose/AUC _{inf.}	М
V/F	Apparent volume of distribution for extravascular dosing	Apparent volume of distribution, estimated from terminal phase, for extravascular dosing.	М
Ae	Cumulative amount of drug recovered unchanged in urine	Sum of amount excreted for each collection period (Urine Concentration * Volume of Urine).	N, M
Ae%	Cumulative amount of drug recovered unchanged in urine, expressed as percent of dose	$100 \times (Ae/Dose).$	М
		Ae/AUC.	

Table 6.Derivation of PK Parameters

Actual PK sampling times will be used in the derivation of PK parameters.

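### NMN Cmax and Tmax do not exclude the predose sample, so a value taken before PF-04965842 can become the modelled Cmax; in expectation this pulls the Test/Reference ratio slightly toward 1 when there is a real effect

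*SAP*

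**What the plan says.** - **Derivation.** SAP 6.3.1 states that parameters are "calculated by treatment and by analyte (if applicable) from the concentration-time data and urine concentrations using standard noncompartmental methods". Its Table 2 marks NMN Cmax for the statistical model on the natural-log scale, and NMN Tmax for descriptive display. Protocol 9.4.4.2, Table 6, assigns the same Cmax and Tmax rows to NMN and metformin: Cmax is "Observed directly from data" and Tmax is "Observed directly from data as time of first occurrence".
- **Sampling.** Protocol 1.3, Table 2, schedules "PK blood sampling for NMN" at 0, 0.5, 1, 2, 4, 6, 8, 12, 16 and 24 h in both periods. Footnote a describes hour 0 as "Predose (metformin administration) sample collection". In Treatment B, "metformin will be administered with PF-04965842 concomitantly in no specific order, over no more than 5 minutes apart" (Table 1, footnote h), so hour 0 also precedes the first PF-04965842 dose.
- **Analyte.** The Synopsis calls NMN "a metabolite of niacin, has been reported to be an endogenous biomarker for assessing MATE/OCT2 inhibition".
- **Analysis.** SAP 8.2 models NMN AUC24, Cmax and CLr as Test/Reference ratios with 90% confidence intervals.
- **Exclusions.** SAP 5.6 and 7.2 cover sampling-time deviations, missing samples and anomalous concentrations. SAP 7.3 covers parameters that cannot be calculated or are known to be biased. SAP 6.4 lists no covariates. None of these deals with an ordinary predose NMN value.

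**The concern.** The rule suits metformin. With a plasma half-life of about 6 h and at least 4 days between doses (96/6 = 16 half-lives), its hour-0 concentration cannot compete to be the maximum. NMN is already circulating at hour 0, so that sample is one of ten candidates. When it is the highest, the modelled Cmax is a value that PF-04965842 could not have influenced, and Tmax is reported as 0.

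What is at stake is modest. NMN is included to explore its use as a marker of MATE activity, and Cmax is one of three NMN parameters modelled. A pull toward 1 would make plasma NMN look slightly less responsive than it is. The plan's silence also lets two analysts derive different NMN Cmax values from the same data.

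**Working it through.** **1. A planned figure, for scale.** The documents give no precision figure for NMN. For metformin Cmax, Protocol 9.2 states a half-width of ±0.161 on the log scale (N = 12, within-participant SD 0.188, 80% coverage probability). It reproduces as t(0.95; 10 df) × SD × √(2/12) × √(χ²(0.80; 10)/10) = 1.812 × 0.188 × 0.408 × 1.159 = 0.161.

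**2. Direction.** Let B be the predose log value, M the postdose log maximum without drug, and θ a constant postdose log effect. The expected all-sample log ratio is

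g(θ) = E[max(B, M + θ)] − E[max(B, M)].

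Its derivative is P(M + θ > B), which lies between 0 and 1. So g(0) = 0, g has the sign of θ, and |g(θ)| ≤ |θ|: no bias without an effect, and a pull toward 1 with one. This is a statement about expectations. Each period has its own predose sample, so a high Test-period predose value can raise an individual ratio.

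**3. How often hour 0 is the maximum.** If NMN is flat, the ten Reference samples are exchangeable and hour 0 is the highest in 1/10 of Reference periods, about 1.2 of 12.

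**4. Size, under stated assumptions.**
- Effect: a rise that grows linearly to 16% at 4 h, then decays with a 4 h half-life. The 16% is illustrative. It takes metformin's renal clearance of 3.5 times creatinine clearance (Protocol 4.3) as a secretory share of 1 − 1/3.5 = 0.714, and an unbound Cmax/IC50 of 0.24 for MATE1 (Protocol 4.2). Then CLr falls to 1 − 0.714 × (1 − 1/1.24) = 0.862, and 1/0.862 = 1.16.
- Noise: independent log-normal variation between samples, CV 5, 10 or 15%.
- Daily pattern: varied as in the table.
- Method: 400,000 simulated profile pairs per scenario at the ten protocol times. Each cell shows the geometric mean ratio of Cmax from postdose samples → from all samples, and the share of the apparent rise lost (from unrounded ratios).

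| Assumed NMN pattern | CV 5% | CV 10% | CV 15% |
|---|---|---|---|
| Flat | 1.098 → 1.095 (3%) | 1.080 → 1.076 (6%) | 1.073 → 1.068 (7%) |
| Smooth 24 h cycle, peak at hours 0 and 24, 10% above trough | 1.090 → 1.084 (6.5%) | 1.077 → 1.070 (9%) | 1.072 → 1.065 (10%) |
| Same cycle, 20% above trough | 1.076 → 1.069 (9%) | 1.070 → 1.062 (12%) | 1.068 → 1.060 (12%) |
| Hour 0 alone 10% lower | 1.098 → 1.098 (0%) | 1.080 → 1.080 (1%) | 1.073 → 1.072 (2%) |
| Hour 0 alone 10% higher | 1.098 → 1.063 (35%) | 1.080 → 1.062 (22%) | 1.074 → 1.061 (18%) |
| Hour 0 alone 20% higher | 1.098 → 1.018 (82%) | 1.080 → 1.041 (48%) | 1.073 → 1.049 (34%) |

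If a 10-20% smooth cycle peaks 6 or 12 h after dosing, the loss is about 0-5%. In the flat and dosing-time-cycle rows the ratio shifts by 0.003 to 0.008. That is at most about 0.008/0.161 = 5% of the planned half-width for metformin Cmax, the nearest available yardstick.

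**The case against.** **No sentence says the predose sample is eligible.** True. Inclusion follows from the literal definition and the absence of any restriction. Nothing in either document points the other way. SAP 7.3 does not help: treating a predose maximum as a known biased estimate would drop that value from the analysis rather than replace it with the postdose maximum.

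**A reader might infer that a third to four-fifths of the NMN signal could be lost.** The last two table rows show losses of 18-82%, but they raise hour 0 alone and return NMN to baseline by 0.5 h. The 24 h sample falls at the same clock time as hour 0 (dosing at about 08:00), so a morning elevation should appear there too. No passage supports such an isolated step. If both hour 0 and 24 h stand 20% high at CV 5%, the postdose-only ratio is itself just 1.021, against 1.009 with hour 0 included, so the fix recovers little.

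**The fix does not make Cmax a sharp measure.** Correct. The maximum of noisy samples turns a 16% peak rise into 7-10% even postdose only with flat NMN. The 0.5 h and 1 h samples also remain, although median PF-04965842 Tmax for the fed tablet was 4.0 h (400 mg dose, Protocol 2.2.4.2.1).

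**Nothing important depends on it.** Largely correct. The biomarker rationale and the planned correlation with metformin rest on CLr. Protocol 4.2 expects little or no effect of MATE inhibition on plasma exposure, and with no effect there is no bias. SAP 4.1 and 4.2 set no hypotheses or decision rules. This limits the severity but does not make a pre-drug value a sensible endpoint.

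**Conclusion.** The point holds as a low-severity defect in an exploratory parameter. Read literally, the plan lets an NMN value taken before PF-04965842 serve as the modelled Cmax, with Tmax of 0, and in expectation this attenuates a real effect. Under an assumed 16% peak rise and CV of 5-15%, the loss is about 3-7% of the apparent rise if NMN is flat, about 6-12% with a smooth cycle peaking at dosing time, and near zero if predose NMN is lower. It is larger only if the predose sample stands well above the postdose ones. All of these figures rest on assumed NMN variability and daily patterns, and the 16% borrows metformin's secretory share for a different molecule.

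Two stronger inferences are not supported. The predose sample does not always shrink the observed ratio, because the result holds only in expectation. Nor is the study's assessment of MATE inhibition compromised: metformin CLr, AUC and Cmax are untouched, the NMN-metformin correlation uses CLr, and within NMN AUC24 (and hence NMN CLr) hour 0 properly anchors only the 0-0.5 h segment.

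**What to change.** In SAP 6.3.1, Table 2, and Protocol Table 6, define NMN Cmax and Tmax over postdose samples only (0.5 to 24 h). Keep the hour-0 sample as the starting point of NMN AUC24. Leave metformin Cmax and Tmax as they are.

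The cost is one sentence in the SAP and one line in the parameter derivation. It needs no new samples and no change to the model. Protocol Section 9 allows the SAP to modify the planned analyses and calls for a protocol amendment only for major changes to the primary endpoint, so the SAP text can carry the change by itself, provided it is settled before database lock.
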